5.1 Major protocol deviations

Based on the ITT analysis set major protocol violations will be summarized (n and %) for each category of protocol violation, by treatment and in total.

5.2 Listing

Based on the ITT analysis set subjects with minor or major protocol deviations will be listed and the list will be sorted by site, treatment and subject number. The listing will include category and description of protocol deviation.

6 Analysis Sets

6.1 Intention-To-Treat Analysis Set

The intention-to-treat (ITT) analysis set comprises of all randomized subjects. Treatment assignment for summaries and analyses are according to planned treatment.

6.2 Per Protocol Analysis Set

The PP analysis set is defined as all data from the ITT analysis set except data excluded due to major protocol deviations as defined in section 5. As defined in section 5 some protocol violations will lead to exclusion of parts of a subject's data, not the entire subject.

6.3 Safety Analysis Set

The safety analysis set comprises all treated subjects and are analysed according to the actual treatment received. If more than one treatment is received the highest dose of Quinagolide will be used.

7 Trial Population

Unless otherwise specified all tables and listing in this section will be based on the ITT analysis set.

All summaries in this section will be presented by treatments and a total column

Categorical data will be summarised using numbers and percentages in addition to the sum 'all'. The percentages are based on the total number of subjects with a corresponding assessment. Continuous data will be presented, using the number of subjects (n), mean and standard deviation, median, 25th percentile, 75th percentile, minimum and maximum.

7.1 Demographics and Other Baseline Characteristics

7.1.1 Demographics and body measurements

Baseline demographics variables (age, race and ethnic origin, height, weight and BMI) will be summarized.

7.1.2 Vital Signs at Baseline

Baseline (visit 4) vital signs will be summarised as described in section 10.4.1.

7.1.3 History of Disease

The worst endometriosis-related pain on the NRS based on a recall of experience in the past menstrual cycle will be summarized as a categorical variable.

Endometriosis initial diagnosis (time since initial diagnosis, method, stage and documentation of histology of biopsy) will be summarised.

Endometriosis surgical history (Any history (yes/no), time since, method and type of surgery) will be summarised.

Menstrual history and reproductive history will be summarised.

7.2 Medical History

Medical history recorded at screening visit will be coded using Medical Dictionary for Regulatory Activities (MedDRA) version 20.0.

Medical history will be summarised by system organ class (SOC) sorted alphabetically and preferred term (PT) sorted in decreasing frequency of occurrence.

Ongoing and past medical history will be reported separately and the number of subjects with any ongoing or past medical history will be included.

7.3 Prior and Concomitant Medication

Prior and concomitant medication will be summarised by ATC classification 1st level (alphabetically), ATC classification 2nd level (in decreasing order of frequency) and treatment group. These medications will be tabulated separately for:

- 1) Prior medication; i.e. medication taken exclusively prior to treatment (i.e. with stop date before date of first ring insertion);
- 2) Concomitant medication, i.e. medication taken during the treatment period (i.e. medication that was not stopped before date of first ring insertion and not started after the last ring removal.
- 3) Post-treatment medications, i.e. medications starting after the treatment period (i.e. with start after the last IMP removal).

The number of subjects with "any medication" will be included in these tables. If the timing of the dose of a concomitant medication cannot be established in relation to the administration of IMP, it will be considered as concomitant medication.

7.4 Physical Examination

Subjects with abnormalities at any screening, or post-baseline visit will be listed with all physical examination evaluations.

7.5 Listings

Baseline characteristic not listed elsewhere will be listed sorted by site treatment and subject number.

Medical history will be listed sorted by site treatment subject number, SOC and PT.

All medications will be listed by site treatment, subject number, start date, ATC level 1 and ATC level 2.

8 Exposure and Treatment Compliance

All tables in this section will be based on the ITT analysis set.

Categorical data will be summarised using numbers and percentages in addition to the sum 'all', the percentages are based on the total number of subjects with a corresponding assessment. Continuous data will be presented, using the number of subjects (n), mean and standard deviation, median, 25th percentile, 75th percentile, minimum and maximum.

8.1.1 Extent of Exposure

Total extent of exposure will be summarised. Total extent of exposure will be based on information from the vaginal ring administration log. For part A, the total extent of exposure will be the date of ring removal at the end of cycle 4 visit (if this visit is not performed or if no ring removal is performed at this visit the last date of ring removal is used) minus the date of the first ring insertion. For part B the extent of exposure will only be defined if the subject has completed part A and initiated part B (part A is considered completed if end-of cycle 4 visit is performed, part B is considered initiated if a ring is inserted at end-of-cycle 4 visit). The extent of exposure in part B is defined as the date of the last ring removal minus the date of end-of-cycle 4 visit.

Extent of exposure for each cycle (cycle 1 to 8) will also be summarised. Extent of exposure for each cycle will as above be calculated as the difference in ring removal dates and insertion dates.

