## 5.6.2 Assessment of Compliance

Compliance with IMP treatment regimen is assessed by dates of vaginal ring insertion and ring removal for each cycle.

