# 7.2.2.14 Ring Acceptability

The subject will be asked to evaluate the acceptability of the vaginal ring immediately after each time she has inserted and/or removed the ring at the clinic on RM+7 of cycle -1 to cycle 4 (at visits 4, 6, 7, 8 and 10).

At randomization (visit 4), a simplified version of the questionnaire with only one question about ring insertion (see Appendix 1) will be completed by the subject.

At RM+7 visits of cycle 1 to cycle 4 (visits 6, 7, 8 and 10), a full version of the ring acceptability questionnaire should be completed by the subject. The full version of the questionnaire consists of questions related to ring insertion / removal, any feeling of the ring while the ring is in the body, any feeling of the ring during sexual intercourse if applicable and any experience of ring falling out or breaking (see Appendix 1). If it is confirmed that the ring is broken upon removal, a technical complaint form should be completed. If it is noted that the ring has been out of the body for more than 24 hours during the cycle, a medication error should be reported.

The answer must be reviewed by the trial coordinator for the potential reporting of medication error before the subject leaves the clinic.

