# 9.7 Extent of Exposure and Treatment Compliance

The extent of exposure is defined as the number of days between the first ring insertion until removal and will be summarized by cycle and treatment group. The total extent of exposure (across all cycles) will be summarized by treatment group and overall. This will be done both including and excluding known periods of intermittent removals of the vaginal ring if applicable.

The number of days of rescue analgesics use and the percentage of days on rescue analgesics will be similarly summarized.

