8.1.2 Treatment Compliance

The treatment compliance in percent will be summarised. Treatment compliance will be based on information about missed dose from the medication errors log.

The compliance percent will be calculated as 100 times the ratio between the number of days exposed to the ring and the expected number of days exposed to the ring.

For part A: The expected number of days exposed to the ring is; if the subjects completes part A the date of end-of-cycle 4 visit minus the date the first ring insertion; and if the subject discontinues treatment during part A the date of discontinuation minus the date of visit 4. The number of days exposed to the ring is calculated as the expected number of days minus the number of days with missed dose between visit 4 and end-of cycle 4 visit (or if the subject discontinues during part A between visit 4 and date of discontinuation).

For part B: The expected number of days exposed to the ring is, if the subjects completes part B the date of end-of-cycle 8 visit minus the date of end-of-cycle 4 visit, and if the subject discontinues treatment during part B the date of discontinuation minus the date of

Statistical Analysis Plan	Version: 1.0	FERRING
Quinagolide	31MAY2022	PHARMACEUTICALS
FE 999051 trial 000165	CONFIDENTIAL	Page 23 (44)

end-of cycle 4 visit. The number of days exposed to the ring is calculated as the expected number of days minus the number of days with missed dose between end-of cycle 4 visit and end-of-cycle 8 visit (or if the subject discontinues during part B between end-of-cycle 4 visit and date of discontinuation).

Non-compliance with IMP treatment regimen for >20% of days during a non-menstrual period, as defined as a protocol deviation in section 5 will be summarised for each cycle.

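### The SAP's fallback for Part A exposure can select a Part B ring removal date, and its compliance rule departs from the protocol without declaring it

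*SAP*

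**What the plan says.** **Exposure (SAP 8.1.1).** The source is the ring log: "Total extent of exposure will be based on information from the vaginal ring administration log". Part A runs from the first insertion to the removal at the end-of-cycle-4 visit, with this fallback: "if this visit is not performed or if no ring removal is performed at this visit the last date of ring removal is used". Completion and entry are defined separately, both by reference to that visit: "part A is considered completed if end-of cycle 4 visit is performed, part B is considered initiated if a ring is inserted at end-of-cycle 4". For the second part, "The extent of exposure in part B is defined as the date of the last ring removal minus the date of end-of-cycle 4 visit". Exposure per cycle is also a difference between removal and insertion dates.

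**Compliance (SAP 8.1.2).** Here the source changes: "Treatment compliance will be based on information about missed dose from the medication errors log". Exposed days are expected days less logged missed-dose days. For a woman who stops in Part A, expected days run to her discontinuation date.

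**Protocol.** Section 5.6.2 says: "Compliance with IMP treatment regimen is assessed by dates of vaginal ring insertion and ring removal for each cycle". Section 7.4.18 records ring dates for insertions and removals done at the clinic. Section 7.2.2.14 calls for a medication error report if "the ring has been out of the body for more than 24 hours during the cycle". Section 9.7 adds, for the exposure summaries: "This will be done both including and excluding known periods of intermittent removals of the vaginal ring if applicable". SAP 8.1.1 contains no net version.

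**Declared departures.** SAP section 12 covers the early termination, the dropped interim and statistical analyses, the shift and markedly-abnormal tables, and two dropped summaries (the progesterone proportion and the biomarkers). It mentions neither the compliance source nor the net exposure summary.

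**The concern.** The fallback has no upper date. The SAP describes the end of Part B in almost the same words, so a programmer following the text would take the final removal in the log. Entry to Part B requires only that a ring was inserted at the visit, not that one was removed there. The situation can arise: protocol 5.1.1 leaves it to the investigator whether a ring expelled during menses is replaced, and the visit falls on day 6 to 10 of menses.

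For such a woman, Part A and Part B exposure overlap. If she was on placebo in Part A, her Part A total would also include days on quinagolide, because SAP section 3 moves placebo women to active rings in Part B. SAP 10.1 closes the Part A adverse event window at the end-of-cycle-4 visit, so her exposure and event windows would no longer match.

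On compliance, a reader who relies on protocol 5.6.2 would expect a figure from ring dates and would not learn from section 12 that a different source was used. Sections 8.1.1 and 8.1.2 also end a discontinuer's exposed days at different dates.

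**Working it through.** The plan states no exposure or compliance figure to reproduce, so the check applies its rules to hypothetical women.

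**1. Which branch can go wrong**
- Visit not performed: Part A is not complete, so Part B is undefined. The last removal is then a Part A date, and there is no error.
- Visit performed with a removal there: the fallback is not used.
- Visit performed, no removal there, new ring inserted there: Part B is initiated and the last removal lies in Part B. This is the only faulty case.

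**2. Size in that case**

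Assumptions: equal cycles of L days; ring out g = 1 to 7 days before the visit; Part B completed. The range L = 24 to 35 is borrowed from inclusion criterion 11.
- Intended Part A = 4L − g
- Literal Part A = 8L
- Part B = 4L

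| L | Intended Part A | Literal Part A |
|---|---|---|
| 24 | 89 to 95 | 192 |
| 28 | 105 to 111 | 224 |
| 35 | 133 to 139 | 280 |

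The ratio is about 2.0 to 2.2. For L = 28, the two parts sum to 224 + 112 = 336 days, against 8 × 28 − g = 217 to 223 days actually worn. SAP 8.1.2 would give the same woman 4 × 28 = 112 expected days in Part A, half the 224 that 8.1.1 reports.

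This is a maximum. If she leaves after one Part B cycle, literal Part A is 5 × 28 = 140 days against 105 to 111.

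**3. End date for discontinuers**

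Suppose the ring is removed on day 28, discontinuation is dated 7 days later (an assumption) and no missed dose is logged. Section 8.1.1 gives 28 exposed days and 8.1.2 gives 35. The same quantity takes two values within one SAP.

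**4. Direction of the compliance departure**
- Home outage of 2 to 7 days in 112, logged: the log rule gives 110/112 = 98.2% down to 105/112 = 93.8%. Clinic dates alone give 100%, so the log rule is the lower one.
- An absence visible in the ring dates but not entered as a missed dose: the log rule is the higher one.
- Outages of 24 hours or less: they need not be reported as medication errors and leave no clinic date, so neither source is sure to show them.

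The sign therefore depends on what was logged.

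**The case against.** The other side has substantial points.

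- The fallback sentence opens with Part A, so a sensible programmer might stop at the last Part A removal. That is possible, but the text does not say it, and the nearly identical phrase for Part B plainly means the final removal.
- The faulty case needs three conditions together, and women under protocol version 6.0 had no Part B. Exposure per cycle is summarised separately and SAP 8.1.3 lists both logs, so an odd value could be spotted. All of this stands, and it is why the point is minor.
- Protocol 9.7 asks for the net summary only where applicable, and 8.1.2 already nets out missed doses, though only as a percentage. That softens the omission but does not declare it.

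A reader might also infer three stronger things that the documents do not support.

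- *That these rules all inflate ring use.* The log exists to catch home outages that clinic dates miss, so the compliance difference can go either way.
- *That the discontinuer above was really 28/35 = 80% compliant and is misreported as 100%.* Once expected days also end at the last removal, she is 28/28 = 100%. The 7-day gap is itself assumed: the protocol's 7 days are a preferred window for the end-of-treatment visit, not a definition of the discontinuation date.
- *That the 8.1.2 percentage drives per-protocol exclusions.* The rule on more than 20% non-compliance (SAP section 5) applies to a non-menstrual period within a cycle. The SAP does not say that it is derived from the percentage over the whole of Part A or Part B.

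**Conclusion.** The point holds as a minor one. Read literally, the Part A fallback gives a wrong exposure for a woman who comes to the end-of-cycle-4 visit without a ring and has one inserted there: up to 224 days instead of 105 to 111 with 28-day cycles. This rests on equal cycles, a gap of 1 to 7 days and completion of Part B. Women with no Part B, or with a removal at the visit, are unaffected, and the documents do not show how many fall in the faulty case.

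The compliance source differs from protocol 5.6.2, the end date for discontinuers differs between SAP 8.1.1 and 8.1.2, and the net exposure summary in protocol 9.7 is absent. The SAP does not declare the compliance change or the missing summary. No direction can be assigned to the compliance difference.

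The consequences stay within the descriptive exposure and compliance summaries. No hypothesis test is planned, and the adverse event tables report subjects, percentages and event counts rather than rates per exposure time. With few women per group, one doubled value could still visibly move a group mean or maximum.

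One limit remains: the SAP makes protocol version 5.0 the basis for the report, but only version 6.0, which has no Part B, was available for checking.

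**What to change.** 1. In SAP 8.1.1, replace the fallback with: the last ring removal on or before the end-of-cycle-4 visit (or discontinuation).
2. In SAP 8.1.2, derive days of wear from the ring administration log minus outages in the medication errors log. An outage already visible as a gap between a removal and the next insertion should be subtracted only once.
3. Use one end date for discontinuers in both sections, and state how the discontinuation date relates to the last ring removal.
4. Add the exposure summary that excludes known intermittent removals, as in protocol 9.7.
5. If items 2 or 4 are not adopted, list the departures from protocol 5.6.2 and 9.7 in SAP section 12.

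The cost is a few lines of SAP text, the derivation code and one added summary. Both logs are already collected and listed, so no new data are needed.

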8.1.2 Treatment Compliance

The treatment compliance in percent will be summarised. Treatment compliance will be based on information about missed dose from the medication errors log.

The compliance percent will be calculated as 100 times the ratio between the number of days exposed to the ring and the expected number of days exposed to the ring.

For part A: The expected number of days exposed to the ring is; if the subjects completes part A the date of end-of-cycle 4 visit minus the date the first ring insertion; and if the subject discontinues treatment during part A the date of discontinuation minus the date of visit 4. The number of days exposed to the ring is calculated as the expected number of days minus the number of days with missed dose between visit 4 and end-of cycle 4 visit (or if the subject discontinues during part A between visit 4 and date of discontinuation).

For part B: The expected number of days exposed to the ring is, if the subjects completes part B the date of end-of-cycle 8 visit minus the date of end-of-cycle 4 visit, and if the subject discontinues treatment during part B the date of discontinuation minus the date of

Statistical Analysis Plan	Version: 1.0	FERRING
Quinagolide	31MAY2022	PHARMACEUTICALS
FE 999051 trial 000165	CONFIDENTIAL	Page 23 (44)

end-of cycle 4 visit. The number of days exposed to the ring is calculated as the expected number of days minus the number of days with missed dose between end-of cycle 4 visit and end-of-cycle 8 visit (or if the subject discontinues during part B between end-of-cycle 4 visit and date of discontinuation).

Non-compliance with IMP treatment regimen for >20% of days during a non-menstrual period, as defined as a protocol deviation in section 5 will be summarised for each cycle.

8.1.3 Listings

Based on the safety analysis set subjects the exposure data from the vaginal ring administration log and the medication errors log will be listed and the list will be sorted by site, treatment, subject number, and date. The listing will include information on dose, dates of insertion and removals, and type and timing of medication error.

9 Efficacy

9.1 Transformation of daily e-Diary data

Subjects will be ask to fill in the daily e-Diary every day from visit 1 to end-of-trial visit. Every night between 8 pm and 2 am the subject should answer the following question:

Instructions and the question to be answered are:

Please think about the **worst** endometriosis-related pain you experienced in the past 24 hours and rate it on a scale from 0 to 10 where 0 is 'no pain' and 10 is 'worst imaginable pain'. Please do not include pain from sexual intercourse.

1. Please rate your **worst** endometriosis-related pain in the past 24 hours (including pelvic pain, abdominal pain, or lower back pain, whichever is the worst).

` D		¹ □ [′]			Í			Í 🗆		
0	1	2	3	4	5	6	7	8	9	10
No										Worst
pain										imaginable
										pain

2. Did you have sexual intercourse in the past 24 hours?

🗆 No

□ Yes

If the subject did not have sexual intercourse in the past 24 hours:

3. Did you **avoid** sexual intercourse in the past 24 hours because of expected endometriosis-related pain?

 \Box No \Box Yes

If the subject had sexual intercourse in the past 24 hours:

4. Pleas	e rate y	our wor	st pain	during o	r after s	exual in	tercours	e in the	past 24	hours.
0	1	2	3	4	5	6	7	8	9	10
No										Worst
pain										imaginable
										pain

5. How did your endometriosis-related pain limit your sitting, standing and walking in the past 24 hours?

Statistical Analys Quinagolide FE 999051 trial 0	is Plan 00165			V 31 CON	ersion: 1 MAY202 FIDENT	0 22 TIAL				FERRING PHARMACEUTICALS Page 25 (44)
□ 0 No limitations on activities	□ 1	□ 2	□ 3	□ 4	□ 5	6	□ 7	8	□ 9	□ 10 Unable to do activities
6. How did y such as doing □	our en g chore	dometri s, launc	osis-rel lry, coo □	ated pai king, w	in limit ashing o	your da lishes, c	ily activ or cleani □	ities ard ng in th □	ound th	e house, 24 hours? □
0 No limitations on activities	1	2	3	4	5	6	7	8	9	10 Unable to do activities
7. How did v	our en	dometri	osis-rel	ated pai	n limit	vour wo	ork/scho	ol in th	e past 2	4 hours?
□ Not appli □ 0 No limitations on activities	cable,≓ □ 1	no work	c or sch	ool in th	the past 2 \Box 5	24 hours	s. □ 7	∑ m m □ 8	9	□ 10 Unable to do activities
8. How did v	our en	dometri	osis-rel	ated pai	n limit	vour so	cial activ	vities w	rith fam	ilv or
friends in the ☐ 0 No limitations on activities	past 2 □ 1	4 hours □ 2	? □ 3	□ 4	□ 5	6	□ 7	8	9	10 10 Unable to do activities
9. Did you ha □ No □ Yes	ave vaş	ginal ble	eding i	n the pa	ıst 24 ho	ours?				

If the subject had vaginal bleeding in the past 24 hours:

10. Please describe your bleeding in the past 24 hours.
□ Spotting (tiny amount of blood on underwear or panty liners)
□ Light (requiring 1-3 sanitary pads or tampons per day)

□ Moderate (requiring 4-6 sanitary pads or tampons per day)
 □ Heavy (requiring more than 6 sanitary pads or tampons per day)

- 11. Was your bleeding related to your period (i.e., menstrual bleeding)?
 - □ No
 - \Box Yes

12. Have you taken any medication to reduce your endometriosis-related pain in the past 24 hours?

🗆 No

□ Yes

13. Which medication did you take for your endometriosis-related pain in the past 24 hours? Please answer "No" or "Yes" for each medication listed below.

MOTRIN 200 mg

□ No

□ Yes

Hydrocodone-acetaminophen (prescribed)

🗆 No

□ Yes

Other \Box No

 \square Yes

The subjects will be asked to specify the number of tablets taken for each medication where "yes" is selected: "Please specify the number of tablets you took."

<An arrow spin will be available to list the number of tablets for each medication where "yes" is ticked.>

If the subject did not answer the diary yesterday:

14. Please let us know why you did not complete the diary yesterday.

- \Box I was in too much pain from endometriosis
- \Box I forgot

 \Box Other reason

